7.12 Treatment with Other Blood Products

Subjects will be treated for hemophilia A exclusively with Alphanate® during the course of the study. If whole blood or other blood products are used during surgery or during the control of hemorrhagic episodes, the exact dose, date and duration of treatment and prescription etiology will be entered in the appropriate case report forms.

7.13 Concurrent Medication

All prescription and non-prescription medication administered to the subjects, including the name of the drug, dose, duration of treatment as well as the indication for use will be entered on the appropriate case report forms.

7.14 Discontinuation of Subjects

A subject will be discontinued from the study if any of the following occurs:

Contains Confidential and Proprietary Information of Grifols Inc.

- A severe or serious adverse event, which, based on medical judgment, prevents completion of participation in the study (See Section 10 for classification of adverse events).
- Development of a Factor VIII inhibitor either
 - at a titer at or above 5 BU/mL **or**
 - at a titer lower than 5 BU/mL but that renders Alphanate[®] treatment ineffective in providing hemostasis.
- Treatment of the subject with another Factor VIII concentrate while in the study.
- Treatment of the subject with immunosuppressive drugs.
- Unwillingness and non-compliance of the subject with the provisions of the protocol.
- Withdrawal of the subject from the study on his/her own volition.
- Death of the subject during participation in the study.

If a subject withdraws after treatment, the clinical site will attempt to obtain all possible follow-up safety data from that subject.

8 CLINICAL ENDPOINTS

The safety of Alphanate[®] will be evaluated based on the following criteria:

8.1 Primary Endpoint

Incidence of antibody inhibitors to Factor VIII in at least 50 evaluable subjects will be determined following a period of at least two years and a minimum of 50 exposure days or if 50 exposure days are not reached, a maximum of 30 months. Only one exposure-day will be accrued for each surgical episode independent of the number of days of treatment or the number of infusions. For the purpose of this endpoint only, a subject is determined to be evaluable when his clinical experience after the date of enrollment includes at least 50 CEDs of treatment with Alphanate[®] or when he develops inhibitors with a titer greater than or equal to 5 BU/mL as determined by the central reference laboratory.

Contains Confidential and Proprietary Information of Grifols Inc.

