4 STUDY DESIGN

This is a phase IV, non-randomized, multicenter study involving at least 50 evaluable subjects diagnosed with severe hemophilia A (levels of Factor VIII:C in plasma less than 0.01 IU/mL), who are male, at least six years of age and not more than 65 years of age, and with a Karnofsky Performance Score of at least 50. All subjects will have adequate immune system function (CD4 count must be greater than or equal to 400 cells/µL and subject must not have an immune system impairment or damage by disease or treatment).

Contains Confidential and Proprietary Information of Grifols Inc.

Enrolled subjects will be treated at home and with in-clinic therapy exclusively with Alphanate[®] as their sole source of FVIII concentrate for prophylaxis and treatment of all bleeding episodes and surgical procedures for a period of at least two years and a minimum of 50 exposure days, or, if 50 exposure days are not reached, for a maximum of 30 months. Alphanate[®] will be administered in accordance with the subject's usual pre-study treatment regimen. An exposure day is defined as any day on which a subject receives one or more infusions of any Factor VIII containing product. However, only one exposure day will be accrued for each surgical episode, regardless of the number of days of treatment or the number of infusions of Factor VIII associated with that surgical procedure.

A subject will continue treatment, as specified above, unless

- The subject develops inhibitors to Factor VIII at a titer greater than or equal to 5 Bethesda units (BU/mL);
- treatment with Factor VIII becomes ineffective at providing hemostasis even for a subject who has developed inhibitors with a titer of less than 5 BU/mL; or
- the subject exhibits severe or serious adverse events that prevent completion of participation in the study.

In all instances, only the inhibitor titer obtained by the central reference laboratory will be used to determine the subject's eligibility to continue his participation in the trial.

The primary endpoint of this study is:

the incidence of Factor VIII inhibitor after exposure to Alphanate[®].

The secondary endpoints are:

1. The frequency, nature, causality and severity of adverse events.
2. The occurrence of changes in biochemical parameters which would indicate alterations in renal or hepatic function.

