Surgery requires that the Factor VIII level be raised to 0.50 to 0.80 IU/mL with the level maintained at or above 0.30 IU/mL for approximately two weeks postoperatively. For dental extractions, the Factor VIII level should be raised to 0.50 IU/mL immediately prior to the procedure; further Factor VIII may be given if bleeding recurs.²⁰

In subjects who experience frequent hemorrhages, Antihemophilic Factor (Human), Alphanate®, may be administered prophylactically on a daily or every other day schedule to raise the Factor VIII level to approximately 0.15 IU/mL.²¹

In pediatric subjects, no clinical trials for safety and effectiveness have been conducted in 16 years of age or younger. Across well-controlled half-life and recovery clinical trials in patients previously treated with Factor VIII concentrates for Hemophilia A, the one pediatric subject receiving Alphanate® (Solvent/Detergent) responded similarly when compared with 12 adult subjects.²²

Contains Confidential and Proprietary Information of Grifols Inc.

Factor VIII levels should be monitored periodically to evaluate the response of individual patients to a given dosage regime.

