9 STATISTICAL PLAN

9.1 Sample Size

The sample size of 50 to 80 evaluable patients followed for at least two years for renal or hepatic function and evidence of seroconversion to HIV-1/HIV-2, HAV, HBV, HCV and parvovirus B19 is in accordance with the recommendations of the CPMP regarding post-authorization surveillance of previously-treated patients infused with a coagulation factor concentrate:

- for which a marketing authorization has already been granted and
- in the production of which a manufacturing process has been added.

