9.2 Planned Method of Analysis

9.2.1 Primary Endpoint

Incidence of Antibody Inhibitors to Factor VIII in Individuals Treated with Alphanate[®]

Assuming a maximum biannual rate of inhibitor incidence of three percent in multi-transfused hemophilia patients, the 95% one-sided confidence interval for this incidence rate in a sample of 50 subjects is up to two percent. Thus,

Contains Confidential and Proprietary Information of Grifols Inc.

with a sample of 50 evaluable subjects monitored for two years, if one subject develops an antibody inhibitor to Factor VIII with a titer higher than 0.6 modified BU/mL, that persists for at least one month, the incidence of inhibitors to Factor VIII will be judged to be higher than that for patients with hemophilia A who are treated with currently marketed Factor VIII concentrates. If the sample size is increased to 80 subjects, no more than 1 subject may develop an antibody inhibitor to Factor VIII.

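### Evaluability for the primary endpoint needs no minimum follow-up, the verdict assumes two years of monitoring, and the SAP uses a third denominator without person-time

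*Protocol*

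**What the plan says.** Protocol 8.1 contains two rules. Its first sentence determines incidence "following a period of at least two years and a minimum of 50 exposure days or if 50 exposure days are not reached", after a maximum of 30 months. Section 4 gives the same treatment period: two years with "a minimum of 50 exposure days, or, if 50 exposure days are not reached, for a maximum of 30 months". So ending at 30 months without 50 exposure days is a planned way to finish.

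The last sentence of 8.1 then defines who is evaluable for this endpoint: "a subject is determined to be evaluable when his clinical experience after the date of enrollment includes at least 50 CEDs" of Alphanate, "or when he develops inhibitors with a titer greater than or equal to 5 BU/mL" according to the central laboratory. Neither route mentions time on study.

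The decision rule in Protocol 9.2.1, repeated in SAP 4, works "with a sample of 50 evaluable subjects monitored for two years" and sets the result against a maximum biannual inhibitor rate of three percent.

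The SAP neither defines nor uses an evaluable set. SAP 9.1 analyses the primary endpoint on the Safety Population by counts and percentages. SAP 5.1 excludes no treated patient from that population.

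**The concern.** The benchmark is a rate over time, so the result set against it should reflect time observed. For an inhibitor-free subject, 8.1 asks only for exposure. On prophylaxis that comes quickly: section 7.9.2 says the product "may be administered prophylactically on a daily or every other day schedule", which gives 50 exposure days in 50 to 100 days. Section 7.14 lists several ways to leave after that, including voluntary withdrawal, non-compliance, use of another concentrate and an adverse event. Such a subject meets the definition with a few months of observation.

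In the other direction, a subject treated only when he bleeds may complete 30 months and remain non-evaluable. Only one exposure day accrues per surgical episode, which makes the threshold harder to reach.

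At stake is a pass/fail safety verdict that turns on a single case at 50 subjects. Two analysts following the documents could use different denominators. The SAP's percentage would show neither of them how much observation lay behind it.

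**Working it through.** **Inputs from the documents:** 50 evaluable subjects; two years each; 3% biannual rate, read as per 24 months (9.2.1, SAP 4); 50 CEDs (8.1); daily or every-other-day prophylaxis (7.9.2).

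**Assumptions:** constant hazard over calendar time; leavers depart inhibitor-free at month 4. The documents give no dropout rate, so the numbers of leavers are illustrative.

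**The plan's own figure.** Both documents state a one-sided 95% interval of up to two percent for 50 subjects. It is not reproduced: the exact one-sided upper bound is 1 − 0.05^(1/50) = 5.8% with no case and 9.1% with one. Two percent equals the raw proportion 1/50. This is a separate matter, and nothing below relies on it.

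**Time to 50 CEDs**
- Daily: 50 days, about 1.6 months.
- Every other day: 100 days, about 3.3 months.
- Three a week (assumed): 50/3 = 16.7 weeks, about 3.8 months.
- To reach 50 within 30 months takes 50/2.5 = 20 a year. A subject with 49 has 19.6 a year and misses.

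**Two inhibitor-free subjects under each rule**
- Leaves at month 4 with 50 CEDs: evaluable by the last sentence of 8.1; short of the period in its first sentence; unclear under 9.2.1; in the SAP denominator.
- Completes 30 months with 49 CEDs: not evaluable by the last sentence; covered by the first; not among the evaluable subjects of 9.2.1; in the SAP denominator.

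**Effect of short follow-up**
- Risk over m months is 1 − 0.97^(m/24). For m = 4 this is 0.51%, against 3% over 24 months.
- With k leavers at month 4, patient-years are 2(50 − k) + k × 4/12, and P(no case) = 0.97^[(50 − k) + k × 4/24].
- k = 0: 100 patient-years; 0.97^50 = 22%.
- k = 5: 91.7 patient-years; 0.97^45.83 = 25%.
- k = 10: 83.3 patient-years; 0.97^41.67 = 28%.
- k = 25: 58.3 patient-years; 0.97^29.17 = 41%.

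**What the bare percentage hides.** One case in 50 is 2% whether or not ten subjects left at month 4. Per patient-year it is 1/100 = 10 per 1,000 with full follow-up, and 1/83.3 = 12 per 1,000 with the ten leavers.

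**Benchmark as a rate.** 3% over two years is 0.03/2, about 15 per 1,000 patient-years.

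**The case against.** Four objections carry weight.

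- A reader might infer that evaluability rests on exposure days alone. It does not: an inhibitor of at least 5 BU/mL also qualifies. Exposure alone decides only for subjects without such an inhibitor.
- A reader might infer that the month-4 leaver is scored in the verdict as a two-year negative. No text says so. Section 9.2.1 can be read as requiring both evaluability and two years of monitoring, and the first sentence of 8.1 supports that reading. What stands is that neither document says which reading applies.
- A reader might infer that the 30-month completer is lost from the reported incidence. Under SAP 5.1 and 9.1 he is in the percentage, as is the early leaver. The evaluability gap affects the evaluable count and the decision rule. The SAP percentage has its own fault: every early leaver, even one treated once, counts as a full negative.
- An exposure criterion has a rationale, since the protocol's introduction describes inhibitor incidence as a function of CEDs in previously untreated patients. If most of the risk falls in the first exposures, a leaver with 50 CEDs has carried most of it. At the limit the chance of zero cases stays at 22%. This limits the size, but the benchmark remains a time rate.

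Section 9.1 is weak support for a two-year inhibitor requirement. Its phrase "The sample size of 50 to 80 evaluable patients followed for at least two years" is tied to renal or hepatic function and seroconversion.

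**Conclusion.** The concern holds as an unreconciled definition. For inhibitor-free subjects 8.1 sets no minimum follow-up, and it leaves out 30-month completers with fewer than 50 CEDs whom its own first sentence covers. The verdict rule assumes two years of monitoring, and the SAP uses a third denominator with no person-time.

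The size is moderate. With 10 of 50 leaving at month 4, observed time falls from 100 to 83 patient-years and the chance of zero cases rises from 22% to 28%. Reaching 41% would need half the sample to leave that early. These figures rest on a constant hazard of 3% per 24 months and on leaver counts that the documents do not supply.

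The net direction is not fixed. Short follow-up makes a clean verdict easier. But 8.1 also admits a subject with an early inhibitor of 5 BU/mL or more while leaving out an inhibitor-free subject who withdraws at the same point, and that raises the proportion. The documents do not support a claim that the reported incidence is known to be too low.

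**What to change.** 1. Reconcile Protocol 8.1 and 9.2.1 with SAP 4, 5.1 and 9.1 on one denominator for the verdict. State the follow-up condition, and say how subjects who complete 30 months with fewer than 50 CEDs are handled.
2. As the figure set against the time-based benchmark, report inhibitors per patient-year, and also per exposure day, in all treated subjects with exact Poisson intervals. Cases and non-cases then contribute only their observed time. Compare with 3% per two years (about 15 per 1,000 patient-years). Cite the 8 per 1,000 patient-years from the protocol's introduction only with the caveat that that cohort was not limited to severe disease: 29 of its 31 cases were severe, whereas this trial enrols severe disease only.
3. Show beside the verdict how many subjects were followed for at least 24 months and how many reached 50 CEDs.

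Do not make the sole basis for the incidence an evaluable set that keeps early inhibitor cases but drops early inhibitor-free leavers. Inclusion would then depend on outcome and push the estimate upward.

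The cost is wording in both documents and one extra table from dates and infusion records already collected. The stated precision may look slightly less favourable. With no cases, the one-sided 95% upper bound is −ln(0.05)/100 = 30 per 1,000 patient-years on full follow-up, and −ln(0.05)/83.3 = 36 per 1,000 in the ten-leaver illustration.

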7.11 Subjects Who Develop Inhibitors

If at any quarterly visit, the subject tests positive for the presence of Factor VIII inhibitors, (inhibitor titer of 0.6 modified BU/mL or greater) based on the local lab test and confirmed by the central reference laboratory test result, the following steps should be taken:

- For an inhibitor titer of greater than or equal to 10 BU/mL,
 - Collect a 10 mL sample of citrated plasma and send to the central reference laboratory.
 - Withdraw the subject only after performing all required testing (see Section 7.4) and only after receiving confirmation of the inhibitor titer from the central reference laboratory.
- For an inhibitor titer less than 10 BU/mL,

Contains Confidential and Proprietary Information of Grifols Inc.

- Collect a 50 mL sample of citrated plasma. This sample can be obtained in multiple draws within a two-week period and sent to the central reference laboratory.
- Repeat inhibitor titer assay at two-week intervals until:
 1. the inhibitor titer decreases to < 0.6 modified BU/mL or
 2. the subject's participation in the study is ended or
 3. it becomes apparent that, after repeated assays at two-week intervals, the inhibitor titer will not decrease during the course of the study (the investigator should first consult with the Project Manager prior to making this determination).
 - If the subject's inhibitor level is less than 5 BU/mL and treatment with Alphanate® at higher doses remains effective in achieving hemostasis, then the subject will continue the current treatment regimen and testing will be performed as described in Section 7.4 above.
 - If Alphanate® treatment either becomes ineffective in achieving hemostasis, even if the inhibitor titer remains below 5 BU/mL, or if the inhibitor level rises to greater than or equal to 5 BU/mL, as confirmed by test results from the central reference laboratory, then the subject will be withdrawn from the study.

Subjects withdrawn from the study may either be treated with alternate concentrates or commence a treatment program with Alphanate® for the induction of immune tolerance. The treating physician, in consultation with Grifols Office of Medical Affairs, will determine the alternate treatment or product and the immune tolerance protocol.

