4. SAMPLE SIZE CONSIDERATIONS

Assuming a maximum biannual rate of inhibitor incidence of three percent in multi-transfused hemophilia patients, the 95% one-sided confidence interval for this incidence rate in a sample of 50 subjects is up to two percent. Thus, with a sample of 50 evaluable subjects monitored for two years, if one subject develops an antibody inhibitor to Factor VIII with a titer higher than 0.6 modified BU/mL, that persists for at least one month, the incidence of inhibitors to Factor VIII will be judged to be higher than that for patients with hemophilia A who are treated with currently marketed Factor VIII concentrates. If the sample size is increased to 80 subjects, no more than 1 subject may develop an antibody inhibitor to Factor VIII.

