5. ANALYSIS POPULATIONS

5.1 Safety Population

The safety analysis population consists of all patients who were randomized and received at least one Alphanate® treatment; no treated patients will be excluded from the safety analysis population.

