9. STATISTICAL ANALYSIS

9.1 Primary Analysis

Analysis of the primary safety endpoint will be conducted on the Safety Population. The primary safety endpoint, presence/absence of Factor VIII inhibitors, will be summarized with frequencies and percentages.

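### A persistent inhibitor below 5 BU/mL in a subject with fewer than 50 exposure days meets the decision rule's case definition but, on the more literal reading, falls outside the rule's count

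*Protocol*

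**What the plan says.** Protocol 8.1 defines evaluability for the primary endpoint alone. There are two routes in: at least 50 CEDs on Alphanate after enrollment, "or when he develops inhibitors with a titer greater than or equal to 5 BU/mL as determined by the central reference laboratory". The first sentence of the same section also allows for a subject who never reaches 50 CEDs and is followed to a cap of 30 months.

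Protocol 9.2.1 sets the decision rule. Its event is a subject who "develops an antibody inhibitor to Factor VIII with a titer higher than 0.6 modified BU/mL, that persists for at least one month". One such subject among 50 evaluable subjects leads to the judgment that incidence is higher than with marketed concentrates. For the larger size the text says: "If the sample size is increased to 80 subjects, no more than 1 subject may develop an antibody inhibitor to Factor VIII". SAP 4 repeats the rule, again "with a sample of 50 evaluable subjects monitored for two years, if one subject develops an antibody inhibitor to Factor VIII".

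Protocol 7.14 discontinues a subject with an inhibitor of 5 BU/mL or more, and also one with an inhibitor "at a titer lower than 5 BU/mL but that renders" Alphanate ineffective for hemostasis. Protocol 7.11 withdraws on the same grounds. Its two-weekly repeat assays may stop when the subject's "participation in the study is ended".

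On the analysis set, the SAP says: "Analysis of the primary safety endpoint will be conducted on the Safety Population". SAP 5.1 adds that "no treated patients will be excluded from the safety analysis population". The SAP defines no evaluable set, and SAP 9.1 gives the endpoint only as presence or absence of inhibitors.

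**The concern.** The titer that admits a subject with few exposure days to the sample (5 BU/mL) is about eight times the titer that makes him a case (5 / 0.6 = 8.3). Between the two lies a subject whom the protocol itself foresees: an inhibitor below 5 BU/mL that makes treatment ineffective, followed by discontinuation. If he stops before 50 CEDs, he can satisfy the rule's titer and persistence terms and still not belong to the sample it is applied to.

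This rule is the only stated criterion for judging the primary endpoint, and it turns on one or two subjects. The SAP table would include the subject. Nothing says whether the judgment is read from that table or from the evaluable subjects, so the report could show an inhibitor case beside a judgment that omits it.

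**Working it through.** **The plan's own figure.** Protocol 9.2.1 and SAP 4 give a one-sided 95% limit of up to two percent for 50 subjects. I could not reproduce it. The exact one-sided upper limit is 1 - 0.05^(1/50) = 5.8% for 0/50, and 9.1% for 1/50. Two percent is the point estimate 1/50. That is a separate matter, and nothing below uses it.

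**Step 1: the definitions side by side** (Protocol 8.1 and 9.2.1). All these subjects are treated, so all are in the SAP 9.1 table.

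| Subject | Evaluable (8.1)? | Case (9.2.1)? | In the rule's count, read literally? |
|---|---|---|---|
| Persistent titer above 0.6 and below 5, reaches 50 CEDs | Yes | Yes | Yes |
| Titer of 5 or more by central laboratory, any CEDs | Yes | Yes, if persistence is documented | Yes, if a case |
| Persistent titer above 0.6 and below 5, stops before 50 CEDs | No | Yes | No |
| Same titer, reaches month 30 short of 50 CEDs | First sentence of 8.1 suggests yes; evaluability sentence says no | Yes | Undetermined |
| No inhibitor, fewer than 50 CEDs | No | No | Not in the denominator |

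The third row is the gap. The fourth is a contradiction within 8.1.

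**Step 2: can a subject be short of 50 CEDs?** Treatment follows the subject's pre-study regimen (Protocol 4), infusions are given as needed (7.9.1), and a surgical episode counts as one exposure day (4 and 8.1). The accrual needed is:
- by month 24: 50 / 24 = 2.08 CEDs per month
- by month 30: 50 / 30 = 1.67 CEDs per month

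Below these rates a subject is still short. At an assumed 2 CEDs per month, the 50th falls at 50 / 2 = 25 months. The documents give no regimen mix.

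**Step 3: effect of one uncounted case.**
- Size 50, no other case: 0/50 = 0% (not triggered) against 1/51 = 1.96% (triggered).
- Size 80, one other case counted: 1/80 = 1.25% (allowed) against 2/81 = 2.47% (limit of one exceeded).

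**Step 4: sensitivity under assumed shares.** Take the plan's 3% rate as a two-year rate and let a share f of cases fall outside the count, so q = 0.03 x (1 - f). The chance that the rule is met is 1 - (1 - q)^50 at size 50, and 1 - (1 - q)^80 - 80q(1 - q)^79 at size 80.

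| f (assumed) | Size 50, at least 1 case | Size 80, at least 2 cases |
|---|---|---|
| 0 | 78% | 70% |
| 25% | 68% | 54% |
| 50% | 53% | 34% |

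The shares are illustrations. The documents give no basis for choosing one.

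**The case against.** The strongest reply is that the SAP already deals with this. Its primary analysis is on all treated subjects, display 12.13 summarizes positive inhibitor tests, SAP 6.4 calls the analysis primarily descriptive, and no SAP analysis section applies the rule. This stands in part. A reader might infer that the case disappears from the report, and it does not. What remains is that SAP 4 still ties the rule to evaluable subjects, while SAP 9.1 states no titer or persistence criterion and no link to the rule.

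Second, the rule can be read more loosely. Its trigger says only that one subject develops an inhibitor, and the sentence for 80 does not repeat the word evaluable. The literal reading also has a difficulty of its own. A sample monitored for two years would drop a subject withdrawn early at 5 BU/mL or more, whom 8.1 expressly admits. So exclusion is the more literal reading, not a demonstrated intention.

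Third, gap cases may be rare. A subject who stays on effective treatment and reaches 50 CEDs is counted, so it would be wrong to infer that low-titer inhibitors as a class are left out. It would also be wrong to infer that frequent prophylaxis closes the gap. On an assumed uninterrupted every-other-day schedule, a subject withdrawn at the early edge of the month-3 window (day 91 - 10 = 81) has (81 - 1) / 2 + 1 = 41 CEDs, and accrual stops there.

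Finally, a reader might want to count a subject who left before a month's persistence was documented. The 9.2.1 definition does not support that, and doing so would change what a case is.

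**Conclusion.** The mismatch between 8.1 and 9.2.1 is in the text and should be reconciled. On the more literal reading, a treated subject who meets the rule's own case definition can be outside its count. The SAP table includes him but is neither defined in the rule's terms nor linked to the rule. One such subject decides the judgment at 50 if he is the only case, and at 80 if exactly one other is counted.

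Confidence that the rule excludes him is moderate, because the looser reading is available. How often this would happen cannot be determined from the documents. A reader might also infer that the incidence percentage is biased downward. That does not follow, because 8.1 also leaves out subjects without an inhibitor who have fewer than 50 CEDs, so the net direction is unknown.

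**What to change.** 1. Amend Protocol 8.1 and 9.2.1 and SAP 4 so that any treated subject who meets the 9.2.1 titer and persistence definition by the central laboratory counts as a case for the rule, whatever his exposure days.
2. Keep the Safety Population analysis in SAP 9.1, apply the 9.2.1 definition in it, and state that the rule's case count is read from it. Keep 50 or 80 evaluable subjects as the size requirement, define that set in SAP 5, and report its result beside the all-treated one.
3. Reconcile the two sentences of 8.1 on subjects with fewer than 50 CEDs at month 30.

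The cost is a few sentences in each document, using central-laboratory and exposure data already collected. The downside is that the observed incidence or the judgment may be slightly less favorable, because cases are then sought in more subjects than the 50 for which the limit was set. With an assumed 60 treated, all at a 3% risk, the chance of at least one case is 1 - 0.97^60 = 84%, against 78% with 50. No dosing or withdrawal rule changes.
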